7.5.2.1.1 Primary Efficacy Endpoint: Upper Extremity Composite Score

Muscle strength based on the MVIC against a dynamometer will be measured bilaterally in the following upper extremity muscle groups: gross grip, shoulder abductors, elbow flexors, and elbow extensors. The UEC is derived from the sum of the average of the right and left total force values (measured in kg) for each muscle group. The comparison of the two treatment groups will be based on the change from baseline in mean UEC score between SA-ER and placebo using generalized estimating equation (GEE) repeated measures with baseline as a covariate.

Additional UEC-related parameters will serve as tertiary efficacy endpoints. The percent predicted total force values will be determined based on reference equations adjusting for age, gender, height, and weight. The percent predicted force will be calculated for each side and the bilateral percent predicted values will be averaged for each upper extremity muscle group (gross grip, shoulder abductors, elbow flexors, and elbow extensors). The mean of the four averages in percent predicted scores will be calculated to create a percent predicted UEC score, and analyzed relative to baseline to create a UEC mean change in percent predicted score. The change in mean percent predicted UEC score between SA-ER and placebo will be compared using the GEE repeated measures analysis.

7.5.2.1.2 Lower Extremity Composite Score

Muscle strength based on MVIC against a dynamometer will be measured bilaterally in the following lower extremity muscle groups: knee flexors, hip flexors, hip extensors, hip abductors and hip adductors. Each muscle group is the average of the right and left total values (measured in kg). The LEC score is derived from the sum of all muscle groups and is a key secondary endpoint. The percent predicted total force values for the LEC will also be determined and analyzed as a tertiary endpoint. The percent predicted force will be calculated for each side and the bilateral percent predicted values will be averaged for each lower extremity muscle group (knee flexors, hip flexors, hip extensors, hip abductors and hip adductors). The mean of the five averages in percent predicted scores will be calculated to create a percent predicted LEC score, and analyzed relative to baseline to create a LEC mean change in percent predicted score.

7.5.2.2 Knee Extensor Muscle Strength

The knee extensors (quadriceps) are widely recognized to be spared in GNEM relative to other lower extremity muscle groups, making it a defining feature of the disease and instrumental in making a differential diagnosis. Knee extensor strength based on MVIC

against a dynamometer will be measured bilaterally as described in Section 7.5.2.1 and is a key secondary endpoint. The percent predicted total force values for the knee extensors will also be determined and analyzed as a tertiary endpoint.

7.5.2.3 GNEM Functional Activities Scale

The GNEM-FAS (also referred to as HIBM-FAS in some studies) is a disease-specific measure developed to assess the functional impact of changes in muscle strength. The scale consists of 3 domains: mobility (a key secondary endpoint), upper extremity (secondary endpoint), and self-care (tertiary endpoint); scores for each domain and a total score (tertiary endpoint) will be obtained. The GNEM-FAS will be administered at the Baseline Visit and Weeks 8, 16, 24, 32, 40 and 48 (or Early Termination) to evaluate physical functioning. The scale has been developed specifically for patients with GNEM based on feedback received from affected individuals on the impact of the disease on their function. Items in the scale assess the subject's ability to independently perform various activities of living that involve self-care, mobility and use of the upper and lower extremities. The scale will be administered in an interview format by a trained clinician (preferably a licensed physical therapist) and scored after the testing. The physical therapists' role is a combination of observing subjects conducting activities and asking subjects questions to assess performance of these activities.

7.5.2.4 Sit-to-Stand Test

The sit-to-stand test ([Agarwal et al. 2006](#)); ([Ozalevli et al. 2007](#)) will be administered at Screening for training purposes, and each subsequent scheduled study visit through Week 48 (or Early Termination), to assess lower extremity function. The test will be administered by a trained clinician (preferably a licensed physical therapist). The subject will be asked to stand upright from a seated position in a chair, return to a seated position, and then repeat the sequence at a comfortable pace according to their own rhythm for the 30 second duration of the test. Use of an arm chair or a stationary object for leverage will be permitted if preferred by the subject. The number of times the subject can rise from a seated to a standing position in a 30-second period will be recorded as a secondary endpoint.

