6 STUDY OBJECTIVES

Primary Objective: Evaluate the effect of 6 g/day SA-ER treatment of subjects with GNEM on upper extremity muscle strength (UEC score) as measured by dynamometry.

Key Secondary Objectives: Evaluate the effect of 6 g/day of SA-ER treatment of subjects with GNEM on:

- Lower extremity composite muscle strength score (LEC score) as measured by dynamometry
- Muscle strength in the knee extensors as measured by dynamometry
- Physical functioning as measured using the GNEM-FAS mobility domain score

Secondary Objectives: Evaluate the effect of 6 g/day of SA-ER treatment of subjects with GNEM on:

- Physical functioning as measured using the GNEM-FAS upper extremity domain score
- Lower extremity function as measured by a timed sit-to-stand test
- Upper extremity function as measured by a timed weighted arm lift test
- Lower extremity function as measured by distance walked in the 6MWT

Tertiary Objectives: To evaluate the effect of 6 g/day SA-ER treatment of subjects with GNEM on:

- Percent predicted UEC and LEC muscle strength scores as measured by dynamometry
- Muscle strength total force for each individual muscle group comprising the UEC and LEC muscle strength scores, as measured by dynamometry
- Percent predicted in each individual muscle group comprising the UEC and LEC muscle strength scores, as measured by dynamometry
- Percent predicted strength in the knee extensors, as measured by dynamometry
- Physical functioning as measured using the GNEM-FAS total score
- Physical functioning as measured using the GNEM-FAS self-care domain score
- Health-related quality of life as measured by the Individual Neuromuscular Quality of Life Questionnaire (INQoL)
- Investigator-assessed symptom severity as measured by the Clinical Global Impression (CGI) Scale
- Changes in CK as a marker of muscle injury

Drug Concentration Measurements

- Free SA levels in serum
- Free, total, and bound SA levels in urine

Safety Objective: Evaluate the safety of 6 g/day SA-ER treatment of subjects with GNEM.

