7.5.2.6 Six Minute Walk Test

The 6MWT will be administered at the Screening visit to determine eligibility. The 6MWT will be administered once per test day at each subsequent scheduled study visit through Week 48 (or Early Termination). Refer to the Study Reference Manual for detailed instructions on conducting the 6MWT.

The 6MWT will be conducted based on American Thoracic Society guidelines ([ATS/ERS 2002](#)). The course length has been modified to 20 meters to allow consistency across testing sites and the BORG scale will not be utilized. Subjects will be instructed to walk the length of a pre-measured course for 6 consecutive minutes. If applicable, the use of any AFOs in the performance of the 6MWT will be noted. Devices other than AFOs may not be used during the baseline assessment; if a subject's disease progresses substantially during the study and there are safety concerns with performing the 6MWT, then additional devices may be used and must be noted on the CRF. The total distance walked (meters) following the six minute period will be recorded as a secondary endpoint. As an additional secondary endpoint, the percent predicted distance walked (for age and gender) will also be determined based on published normative data ([Gibbons et al. 2001](#)).

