## Sit-to Stand Test (STS)

The STS test is a performance test that requires an individual to rise from a seated position as many times as possible in a 30-second period with the score recorded as the number of repetitions completed. Performance of this test requires the use of various lower extremity muscle groups, including the hip extensors, knee extensors, hip adductors, hip flexors and knee flexors. Each of these muscle groups makes a different contribution depending on the stage of the maneuver. Given that all of the muscle groups required to rise from a seated position are being tested using HHD, improved performance on this measure could be used to translate any observed changes in LEC or the individual lower extremity muscle groups into clinically meaningful benefit to the patient. The ability to rise from a seated position is critical to performance of various daily activities, including toileting and getting out of a car, and is necessary to maintain functional independence.

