#### **8.8.2 Analyses of Other Secondary Endpoints**

No sensitivity analysis will be performed for other secondary endpoints. The rest of the secondary endpoints include changes from baseline to week 48 for the following clinical outcomes:

- GNEM Functional Activities Scale Upper Extremity Domain score: this is a domain of the GNEM Functional Activities Scale reflective of upper extremity muscle strength
- Number of Stands in the Sit-to-Stand Test: Lower extremity function will be assessed using a sit-to-stand test. The number of times the subject can rise from a seated to a standing position in a 30-second period will be recorded.
- Number of Lifts in the 30 second Weighted Arm Lift Test: Upper extremity function will be assessed using a weighted arm lift test performed bilaterally. The number of times the subject can raise a 1 kg weight above the head in a 30-second period will be recorded.
- Meters Walked in the Six-Minute Walk Test: The total distance walked (meters) in a six minute period (6MWT) will be measured as well as the percent predicted distance based on normative data for age and gender.

No adjustment for multiplicity will be performed for these endpoints. Each endpoint will be tested at the 0.05 two sided level of significance and nominal p-values will be reported using the same GEE model as the one for the primary analysis.

Two sets of analyses will be conducted on Functional Activities Scale of upper extremity: one will be on the primary analysis set, and the other will be on the subset of subjects that excludes those subjects with the maximum score at baseline. For example, subjects with a baseline score of 32 in upper extremity will be excluded from the analysis of the upper extremity scale. The same method of analysis model (GEE) as the one for the analysis of the primary endpoints will be used.

In addition, in the subjects with a baseline score less than the maximum of 32 on the GNEM-FAS upper extremity scale, the proportion of subjects in each treatment group who achieve the MID as defined by an increase in UE domain score of at least 1.47 points (GNEM-FAS Dossier) indicating an improvement in UE function or a decrease of at least 1.47 points in UE domain score indicating a decline in UE function or changes between -1.47 and 1.47 will be summarized descriptively as a supportive analysis.

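### A switch from unaided to aided performance in the sit-to-stand test or the six-minute walk can understate leg decline: arm use need not be recorded, and the walking-device note is never used in the analysis

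*Protocol*

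**What the plan says.** **Sit-to-stand.** Protocol Section 6 lists as an objective "Lower extremity function as measured by a timed sit-to-stand test". Protocol 7.5.2.4 then allows support: "Use of an arm chair or a stationary object for leverage will be permitted if preferred by the subject". That section does not restrict the choice to particular visits, require the Baseline method to be kept, or ask for the method to be recorded. The score is a plain count. SAP 8.8.2 says "The number of times the subject can rise from a seated to a standing position in a 30-second period will be recorded". SAP 3.3 gives the reason for the test. It names only hip and knee muscle groups as needed to rise, notes that all of them are measured by dynamometry, and concludes that "improved performance on this measure could be used to translate any observed changes in LEC or the individual lower extremity muscle groups" into patient benefit.

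**6MWT.** Protocol 7.5.2.6 says "Devices other than AFOs may not be used during the baseline assessment". If disease later progresses substantially and the walk raises safety concerns, "then additional devices may be used and must be noted on the CRF". Use of ankle-foot orthoses (AFOs) is noted as well. The endpoint is total metres, aided or not.

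**Analysis.** SAP 8.8.2 analyses both tests as change from baseline to Week 48 with the common GEE model and reports nominal p-values. It states that other secondary endpoints get no sensitivity analysis.

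**The concern.** The two tests are meant to show change in leg function over 48 weeks. A subject who rises unaided at Baseline and pushes up with the arms at Week 48 is doing a different task, yet the two counts are subtracted as if the task were the same. The same applies to a subject who walks unaided at Baseline and with a device later, and the protocol ties that switch to substantial progression. If such switches occur more often in one arm, the treatment comparison is affected. Even if they do not, the descriptive results look more stable than the subjects' legs are.

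Sit-to-stand has a second problem. Grip and the elbow extensors plausibly contribute to pushing up, and both belong to the upper extremity composite (UEC). Once arm leverage is allowed, a change in the count no longer points to the leg muscles alone, which is what the SAP's reasoning requires.

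**Working it through.** The plan gives no standard deviation, effect size or rate of aid use for either test. Its only power figure concerns the UEC, so there is no figure on this point to reproduce. The check is mainly a comparison of the texts.

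| Question | Sit-to-stand | 6MWT |
|---|---|---|
| Baseline unaided? | Not required | Yes, AFOs excepted |
| Aid allowed later? | By subject preference | Substantial progression plus safety concerns |
| Aid recorded? | Not required in the protocol | Yes, on the CRF |
| Aid used in the analysis? | No | No |

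**Could another section close the gap?**
- SAP 4.8 names baseline, gender and region as covariates. It leaves room for unspecified others but names none for aid.
- SAP Appendix 10.4 predicts 6MWT distance from age and gender only.
- The decline imputation in SAP 7.1 names dynamometry endpoints. SAP 8.1 could be read as extending it to all repeated measures, but it fills missing values after early withdrawal. It does not reach a subject who stays in and switches to aid.
- SAP 7.1 and Appendix 10.2 score a dynamometry value as 0 when it is missing because of weakness. The performance tests have no counterpart.

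None of these closes it.

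**One subject (assumed numbers).** Baseline is 8 unaided stands, and at Week 48 the subject cannot rise unaided. If arm support restores the full count, the recorded change is 8 − 8 = 0. If it restores half, the change is 4 − 8 = −4. The unaided change is 0 − 8 = −8. The result is thus maintained function or a smaller decline, depending on how much the support restores.

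**Treatment comparison (assumed numbers).** Take 40 per arm (80 randomised 1:1, all evaluable) and a true standardised difference that gives 80% power: d0 = (1.960 + 0.842) × √(2/40) = 0.626. Let q be the excess proportion of placebo subjects who switch to aid, and g the amount of score that aid restores, in SD units. The observed difference is d = d0 − q × g, and power is approximately Φ(d/√(2/40) − 1.960).

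| q | g | d | Shrinkage | Power |
|---|---|---|---|---|
| 0.05 | 0.5 | 0.601 | 4% | 77% |
| 0.10 | 1.0 | 0.526 | 16% | 65% |
| 0.20 | 1.0 | 0.426 | 32% | 48% |
| 0.30 | 1.0 | 0.326 | 48% | 31% |

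With q = 0 and equal restoration the mean difference does not move, although each aided subject's decline is still understated. The table covers masking only. If treatment raises arm strength, arm-assisted counts could rise on SA-ER and push the sit-to-stand difference the other way.

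**The case against.** Much of the opposing case stands.

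- **Aid need not restore the score.** A reader might infer that progression is always scored as maintained. The documents do not support that: a subject with a walker may still cover fewer metres, and that loss counts. A subject who uses the arms from Baseline onward has no change of mode.
- **The 6MWT is not as exposed as sit-to-stand.** Baseline is unaided, the trigger has two parts, and device and AFO use are already noted. Only the analysis rule is missing.
- **Switching may be uncommon.** Subjects walk at least 200 m unaided at Screening, progression is described as gradual, the quadriceps are relatively spared, and no Phase 2 treatment group showed a significant decline in function.
- **The Study Reference Manual is not available here.** It may fix the chair or record arm use, but it would not supply the missing SAP rule.
- **Other endpoints cover leg decline.** The lower extremity composite, knee extensors and GNEM-FAS mobility are tested separately, and SAP 3.3 already judges the 6MWT unsuitable as a key secondary endpoint.
- **As-performed scoring is defensible.** SAP 3.3 links rising from a chair to daily tasks. Making zero the main score for any aided test would treat a precaution as total inability. At an assumed 400 m baseline, one zero among 40 subjects moves an arm mean by 400/40 = 10 m. That scoring also cannot be applied to visits already done without an arm-use record.

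These points limit the size of the problem and rule out zero scoring as the main analysis. They do not supply the missing sit-to-stand record or the missing analysis rule.

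**Conclusion.** The point holds as a gap in measurement and analysis for two other-secondary endpoints. A change from unaided to aided performance can be scored as no decline or as too small a decline, and the plan has no analysis that would show it. For sit-to-stand, the protocol does not secure the information needed to look.

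The size is unknown. The 4% to 48% shrinkage rests wholly on assumed switching and restoration, so it is a range and not an estimate. A reader might infer a definite bias against the drug. That would need more switching on placebo and no arm-strength effect on the counts, and the documents establish neither, so the net direction for sit-to-stand is open. A reader might also infer a threat to the main efficacy claim. There is none: both endpoints lie outside the Hochberg family and carry nominal p-values, so the primary and key secondary tests are untouched. This is a cheap improvement to the plan, not a defect that endangers it.

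**What to change.** **Protocol 7.5.2.4.** Record arm or object use at every remaining visit. Test in the same mode and chair as at Baseline where the subject can. If the subject can no longer do so, record that fact and the assisted count.

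**SAP 8.8.2.** Keep as-performed values as the main analysis. For these two endpoints, replace the statement that there is no sensitivity analysis with one fixed before unblinding that scores an unaided-to-aided change as decline. A worst-rank score would serve for either test, and 0 unaided stands is an alternative for sit-to-stand. Use the new arm-use record and the device note that the 6MWT already requires. Report the number of aided subjects by arm and visit, with a separate count where the sit-to-stand mode is unknown.

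The safety allowance for devices in Protocol 7.5.2.6 stays as it is.

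**Cost.** One CRF field, a line of test instruction, a few SAP sentences and one extra analysis; no added visit or assessor. Earlier visits without an arm-use record stay as performed, so for subjects already enrolled the sit-to-stand sensitivity analysis will be incomplete. The 6MWT part can use notes already collected.

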7.5.2.5 Weighted Arm Lift Test

Upper extremity function will be assessed using a weighted arm lift test. The weighted arm lift test ([Agarwal et al. 2006](#)) will be administered at the Screening Visit for training purposes, then at each subsequent scheduled visit through Week 48 (or Early Termination). The subject will be asked to sit in a chair holding a 1 kg barbell with the shoulder adducted, the elbow in full flexion, and the forearm in supination. On command, the subject will be asked to lift the arm above the head until the elbow is fully extended, then to lower the arm back to the starting position. The subject will be asked to repeat the action at a comfortable pace according to their own rhythm for the 30 second duration of the test. The test will be performed bilaterally and the final score will be the mean of the total number of completed

repetitions from both arms. The number of times the subject can raise the 1 kg weight above the head in the 30-second test period will be recorded as a secondary endpoint.

7.5.2.6 Six Minute Walk Test

The 6MWT will be administered at the Screening visit to determine eligibility. The 6MWT will be administered once per test day at each subsequent scheduled study visit through Week 48 (or Early Termination). Refer to the Study Reference Manual for detailed instructions on conducting the 6MWT.

The 6MWT will be conducted based on American Thoracic Society guidelines ([ATS/ERS 2002](#)). The course length has been modified to 20 meters to allow consistency across testing sites and the BORG scale will not be utilized. Subjects will be instructed to walk the length of a pre-measured course for 6 consecutive minutes. If applicable, the use of any AFOs in the performance of the 6MWT will be noted. Devices other than AFOs may not be used during the baseline assessment; if a subject's disease progresses substantially during the study and there are safety concerns with performing the 6MWT, then additional devices may be used and must be noted on the CRF. The total distance walked (meters) following the six minute period will be recorded as a secondary endpoint. As an additional secondary endpoint, the percent predicted distance walked (for age and gender) will also be determined based on published normative data ([Gibbons et al. 2001](#)).

7.5.2.7 Individual Neuromuscular Quality of Life Questionnaire

The INQoL ([Vincent et al. 2007](#)), a tertiary endpoint, is an individualized self-report measure of health-related quality of life designed specifically for adults with muscle disease. The INQoL will be administered at the Baseline Visit and Weeks 8, 16, 24, 32, 40, and 48 (or Early Termination). The INQoL will be presented to the subject in paper format for completion prior to the administration of the performance tests. The INQoL is a 45-item measure consisting of ten subscales; four measure the impact of muscle disease symptoms, including weakness, locking (seizing), pain and fatigue of muscles. Five additional subscales evaluate the degree of symptom impact on particular areas of life, including activities, independence, social, emotional, and body image. The final domain assesses perceived and expected treatment effects and will not be administered due to the blinded nature of the study. All responses are given in a seven-point Likert scale, with higher scores indicating greater impact.

The INQoL will only be completed for subjects when a validated version of the scale is available in the subject's native language.

